**Abstract**

Switching from combustible cigarettes to e-cigarette use may be a practical harm reduction strategy for vulnerable groups with a high smoking prevalence and a low likelihood of cessation. There is substantial evidence that offering financial incentives for smoking abstinence is an effective approach for promoting smoking cessation in a variety of challenging populations, nevertheless the majority are still not able to quit. The combination of offering financial incentives to incentivize combustible cigarette abstinence, while offering e-cigarettes as an alternative is a novel and potentially powerful harm reduction approach that may lead to reduced cigarette consumption in a population that is unlikely to quit smoking. The proposed study will provide initial information about the feasibility of using this harm reduction strategy to reduce cigarette consumption among homeless adults. The aims of the proposed study are to: 1) assess the characteristics and needs of Homeless Alliance Day Shelter users (up to 1000 adults), 2) characterize tobacco and e-cigarette use patterns, tobacco history, and past cessation attempts among individuals accessing services at the Homeless Alliance Day Shelter, and 3) assess interest in tobacco cessation and tobacco harm reduction intervention approaches. A sub-study ( $N = 60$ ) will 4) characterize reductions in cigarette smoking, complete cigarette abstinence, e-cigarette use, and dual use of combustible cigarettes and e-cigarettes among Homeless Alliance Day Shelter guests following the provision of: an e-cigarette device and supplies (pods, device charger) or e-cigarette device + financial incentives for combustible cigarette abstinence.

## **A. Specific Aims**

The aims of the proposed study are to: 1) assess characteristics and needs of up to 1000 adult males and females who receive services at the Oklahoma City Homeless Alliance Day Shelter, 2) characterize tobacco and e-cigarette use patterns, tobacco history, and past cessation attempts among individuals using services at the Homeless Alliance Day Shelter, and 3) assess interest in tobacco cessation and tobacco harm reduction intervention approaches. A sub-study (randomized controlled trial;  $N = 60$ ) will: 4) complete cigarette abstinence, e-cigarette use, and dual use of combustible cigarettes and e-cigarettes among Homeless Alliance Day Shelter guests following the provision of an e-cigarette device with nicotine pods and the ability to earn financial incentives for abstaining from combustible cigarettes. Sub-study participants will be randomly assigned to: 1) the provision of an e-cigarette device and supplies/pods through 4 weeks post-switch along with directions to switch over from combustible cigarettes to e-cigarettes exclusively, or 2) the combination of an e-cigarette device and supplies through 4 weeks post-switch and financial rewards to incentivize combustible cigarette abstinence, which is based on a previously developed incentive schedule for socioeconomically disadvantaged and homeless adults. In both groups, cigarette smoking will be monitored over an 8-week period to characterize reductions in cigarette smoking, cigarette abstinence, dual use (combustible cigarettes and e-cigarettes) and rates of exclusive e-cigarette use (i.e., switching). It is anticipated that individuals who are provided with an e-cigarette device and supplies and are also incentivized for combustible cigarette abstinence will show greater reductions in cigarette smoking and be more likely to quit combustible cigarettes and switch to exclusive e-cigarette use. The long-term objectives of the survey are to inform improvements to the services available to Day Shelter users and to identify strategies to help homeless adults quit smoking or reduce harm associated with smoking.

## **B. Background and Significance**

Poor health is commonplace among homeless adults, who suffer mortality rates at least 3 times greater than adults in the general population. Although smoking rates have declined to 13.9% among adults living at or above the poverty threshold in the U.S., the prevalence of smoking is 26.1% among those living in poverty, and at least 70% among homeless adults. Numerous studies have shown that lower socioeconomic status (SES) is associated with a reduced likelihood of smoking cessation, despite a similar number of cessation attempts between individuals of lower and higher SES. Not surprisingly, socioeconomic disadvantage is linked with greater tobacco-related cancer incidence and mortality risk. Although standard cessation approaches are helpful for many, alternative strategies may benefit those who are unable to quit following traditional evidence-based treatment recommendations. Switching from combustible cigarette smoking to e-cigarettes exclusively may be a practical harm reduction strategy for some, especially vulnerable groups with a high smoking prevalence and a reduced likelihood of cessation. The possibility of

utilizing e-cigarettes as a harm reduction tool has become more feasible based on research demonstrating that e-cigarettes are associated with far fewer harmful exposures than cigarette smoking. Nevertheless, serious concern developed over the summer/fall of 2019 about the sudden and rising number of e-cigarette and vaping-related lung injury (EVALI) cases. Recent information indicates that EVALI was primarily associated with THC-containing vaping products acquired from informal sources, which contained the product additive - vitamin E acetate. Since September 2019, EVALI hospital admissions have sharply declined possibly due to increased public awareness of the risks associated with THC-containing e-cigarette use, removal of vitamin E acetate from vaping products, and law enforcement actions taken to reduce the availability of illicit products. In February 2020, the Centers for Disease Control and Prevention (CDC) stopped collecting data on EVALI following the identification of the cause of EVALI and the decline in cases.

There is substantial evidence that offering financial incentives for cigarette abstinence is an effective approach for promoting smoking cessation in a variety of challenging populations. [name] published work as well as findings from her ongoing NIH-funded trial (IRB protocol #6260), indicate that offering small escalating financial incentives for smoking abstinence dramatically increases cessation rates among socioeconomically disadvantaged smokers when incentives are included as an adjunct to standard treatment. The combination of offering both financial incentives for smoking abstinence and e-cigarettes as an alternative to smoking is a novel and potentially powerful harm reduction approach for those who are less likely to quit smoking. The proposed study will provide information about the feasibility of using alternative intervention strategies for socioeconomically disadvantaged and homeless adults who continue to smoke. E-cigarettes, alone or in combination with smoking financial incentives for cigarette abstinence, may be incorporated into existing tobacco cessation programs to decrease the use of combustible cigarettes among socioeconomically disadvantaged smokers. New and innovative approaches are needed to address worsening tobacco-related health disparities.

### **C. Preliminary Studies/Progress Report**

[name] earned her Ph.D. in Clinical Psychology from Louisiana State University in 2007. She is currently an Associate Professor in the Department of Family and Preventive Medicine, and a member of the Cancer Prevention and Control Program of the Stephenson Cancer Center Cancer. [name] leads the Tobacco Treatment Research Program (TTRP), which offers free counseling and pharmacotherapy to adults from campus and the community while collecting data relevant to the process of smoking cessation and facilitating recruitment into research studies (IRB protocol #6951). She has published extensively in the areas of tobacco cessation interventions, behavioral medicine, cancer prevention, and health disparities, and she has a history of external funding from the American Cancer Society (ACS) and the National Cancer Institute (NCI). Notably, [name] previously completed a randomized

controlled trial (RCT) to evaluate the feasibility and short-term effectiveness of offering small financial incentives (gift cards) for biochemically verified abstinence as an adjunct to the tobacco cessation program offered at the Dallas County safety net hospital. [name] also completed an NCI-funded follow-up RCT to evaluate the longer-term impact of an adjunctive, low-cost intervention offering small financial incentives (relative to standard care) on smoking abstinence rates among socioeconomically disadvantaged individuals participating in a clinic-based tobacco cessation program. She is currently conducting an NCI-funded trial of an automated, mobile incentives-based smoking cessation intervention for low-income adults. Notably, [name] has a history of published research directly relevant to tobacco cessation interventions, and especially within socioeconomically disadvantaged populations. She has also conducted tobacco and health-related research within homeless populations specifically. [name] provides expertise related to e-cigarettes and switching from combustible cigarettes to e-cigarettes. [name] is a long-time collaborator of [name], and provides additional expertise related to tobacco cessation intervention in socioeconomically disadvantaged and homeless populations. [name] provides biostatistics expertise, and [name] is a collaborator and trainee of [name] with expertise in tobacco cessation interventions and health disparities.

#### **D. Research Design and Methods**

**Overview.** The current protocol includes a parent survey study, and an intervention sub-study. The parent survey study will assess the characteristics and needs of Homeless Alliance Day Shelter users (up to 1000 adults), 2) characterize tobacco and e-cigarette use patterns, tobacco history, and past cessation attempts among individuals accessing services at the Homeless Alliance Day Shelter, and 3) assess interest in tobacco cessation and harm reduction intervention approaches. Based on responses to screening items assessing eligibility criteria, participants will be identified as eligible for the sub-study. The sub-study ( $N = 60$ ) will 4) characterize reductions in cigarette smoking, smoking abstinence, e-cigarette dual use, and e-cigarette use/switching following randomization to: 1) an e-cigarette device and supplies (device charger, pods) for 4 weeks, or 2) e-cigarette and supplies for 4 weeks + financial incentives for combustible cigarette abstinence among Homeless Alliance Day Shelter guests. Participants will be followed through 8 weeks post-switch date to determine whether they continue to use e-cigarettes when the supplies are no longer provided. Both the parent survey study and intervention sub-study will provide data related to tobacco use, which will be used to support future grant funding applications. Both components of the study will take place at the Homeless Alliance Day Shelter.

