### **Sub-Study.**

Overview. The sub-study will examine the feasibility and preliminary efficacy of providing financial incentives for combustible cigarette abstinence in combination with switching to e-cigarettes among 60 socioeconomically disadvantaged Homeless Alliance day shelter users. A total of 60 adults who access the day shelter will be recruited to participate in the sub-study. Participants will be randomly assigned to one of two groups and followed weekly from 1 week prior to switching through 4 weeks after switching, with a final 8-week post-switch follow-up. The intervention groups are 1) switching to e-cigarettes (EC), or 2) small financial incentives for cigarette abstinence + switching to e-cigarettes (FI + EC). Payments will be made via Greenphire clincard, which is similar to a debit card. The primary outcome will be carbon monoxide (CO)-verified combustible cigarette abstinence (CO) at 4- and 8-weeks post-switch date. Combustible cigarette reduction, EC use/switching, and dual use (cigarettes and ECs) will also be examined.

**Intervention Groups.** All participants will have the opportunity to earn \$20 for completing study assessments at visits 2 through 7 and \$50 for completing visit 8 (see Table 1).

Financial Incentives + E-Cigarettes (FI + EC). At baseline (1-week pre-switch), participants assigned to this group will be provided with an e-cigarette device and they will be offered 7 pods to try. Participants will be encouraged to practice using the device over the subsequent week (before they switch to exclusive use). Participants will be advised to completely switch from combustible cigarettes to

the e-cigarette device one week after the baseline visit. On the switch date, they will be supplied with refill cartridges in the flavor(s) of their choice and based on their pre-switch smoking level. One pod ≈ 200 puffs and provides the amount of nicotine in ≈ 1 pack of cigarettes. Thus, someone who smokes a pack of cigarettes each day may be expected to use about 1 pod per day.

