### **Sub-Study Visits.**

**Recruitment/Screening (Visit 1, Screening & Scheduling).** Eligible participants who complete the screening survey will be given a chance to review the consent form. Study staff will provide the participant with ample time to review the study information and ask questions related to their participation. Participants who enroll will be scheduled to return for a baseline visit (typically within the next 7 days). The Homeless Shelter Alliance case workers, who work

with the shelter's guests, may encourage their clients to enroll and retain participation in the study.

**Baseline (Visit 2).** Enrolled participants will be randomly assigned to the EC or FI + EC condition. Enrolled participants will be asked to provide their personal information (name and phone numbers). Participants will be instructed to switch from combustible cigarettes to e-cigarettes at bedtime or 10:00 pm (whichever occurs first), on the evening prior to their next scheduled weekly session. They will be provided with a EC device and they will have the opportunity to try it out. They will be provided with 7 pods (5% nicotine).. They will keep the pods in order to practice using the e-cigarette device over the week prior to their switch date. Participants will be advised about earning financial incentives for switching to ECs or yoking) beginning the following week on the quit/switch day. The schedule of payments will be discussed with all participants (see Table 1). Participants will be instructed not to use THC-containing vaping products and "street" vaping products, and not to modify or add chemicals to their vaping supplies while they are enrolled in the study. They will be counseled to use only the supplies that they are given by study staff, and to avoid dual use of e-cigarettes and cigarettes or other combustible products, including marijuana. Participants will receive a \$10 Greenphire clincard paymentfor completing this visit and they will be provided with a Tracfone (or similar "burner" phone) along with a prepaid phone plan that will cover the study period to facilitate communication between the participant and study staff. Participants will be encouraged to complete this visit as soon as possible, but it can be completed within 21 days of visit 1. Enrollment into the sub-study will cease once 60 participants are enrolled.

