**Switch Day (Visit 3; 1 week after baseline).** Participants will complete self-report questionnaires on a laptop computer; and expired CO and weight will be measured in a private area of the shelter to ensure confidentiality. Participants assigned to the FI + EC treatment will receive an additional \$20 paymentif their expired CO level is  $\leq 8$  ppm (please note that the less stringent cut-off of 8 ppm will be used to verify abstinence on the first post-switch day only, because of the recency of switching). EC participants will receive the same payment as their yoked FI + EC counterpart. Attempts will be made to contact participants who do not attend study visits, in order to obtain self-reported smoking status. Participants will be supplied with pods in the flavor(s) of their choice, based off of what research staff has available, and based on their pre-switch smoking level.

**1-4 Weeks Post-Switch (Visits 4-7).** Participants will complete self-report questionnaires on a laptop computer; and expired CO and weight will be measured in a private room to ensure confidentiality. Participants randomized to the + EC group will receive an additional \$20-\$40 credit for self-reported abstinence and CO readings  $\leq 6$  ppm. EC participants will receive the same payment as their yoked FI + EC counterpart. Additional pods will be provided at each weekly visit based on pre-switch smoking levels. Participants will be

provided with 1 additional e-cigarette device *only if* they lose or damage the first device. Participants will not be provided with any e-cigarette supplies after visit 7, to determine whether they continue to use the e-cigarette on their own.

**8 Weeks Post-Switch (Visit 8).** Participants will complete self-report questionnaires on a laptop computer; and expired CO and weight will be measured in a private area to ensure confidentiality. Participants will receive a \$50 for completing this final follow-up visit, and participants may keep their study phones. Participants will be advised that they can receive free smoking cessation treatment through the Tobacco Treatment Research Program^36 or the Oklahoma Tobacco Helpline and provided with contact information.

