**Table 1. Sub-study compensation schedule.**

	Assessments	Incentive/ Yoking	Total Possible Earnings
Visit 1 (Brief Screening)	\$0	\$0	\$0
Visit 2 (baseline/enrollment; 1 week pre-switch)	\$20	\$0	\$20
Visit 3 (switch Day)	\$20	\$20	\$40
Visit 4 (1-week post-switch)	\$20	up to \$25	\$45
Visit 5 (2 weeks post-switch)	\$20	up to \$30	\$50
Visit 6 (3 weeks post-switch)	\$20	up to \$35	\$55
Visit 7 (4 weeks post-switch)	\$20	up to \$40	\$60
Visit 8 (8 weeks post-switch)	\$50	\$0	\$50
Total Possible Earnings	\$170	\$150	\$320

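### Week-8 e-cigarette use may partly reflect leftover study pods, and the plan describes no way to tell this from use that participants sustain themselves

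*Combined protocol and SAP*

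**What the plan says.** The Overview in Section D gives a purpose for following participants to week 8: "Participants will be followed through 8 weeks post-switch date to determine whether they continue to use e-cigarettes when the supplies are no longer provided". Sub-Study Visits repeats it: "Participants will not be provided with any e-cigarette supplies after visit 7, to determine whether they continue to use the e-cigarette on their own".

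The supply rules are these:

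- Baseline (visit 2, one week before the switch): "They will be provided with 7 pods (5% nicotine"; and "They will keep the pods in order to practice using the e-cigarette device over the week prior to their switch date". The number is the same for every smoking level.
- Switch day (visit 3): "Participants will be supplied with pods in the flavor(s) of their choice", in an amount set by pre-switch smoking.
- Visits 4 to 7: "Additional pods will be provided at each weekly visit based on pre-switch smoking levels". Table 1 places the last of these at four weeks after the switch ("Visit 7 (4 weeks post-switch").

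On the expected rate of use, the Sub-Study section equates one pod with about one pack of cigarettes: "Thus, someone who smokes a pack of cigarettes each day may be expected to use about 1 pod per day".

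Section G (Sources of Research Material) lists questionnaires, expired CO, height and weight, attendance, and phone contact about tobacco use. It mentions no count or return of pods. Section E analyses e-cigarette use, switching and dual use as secondary outcomes, without regard to where the pods came from.

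**The concern.** If the aim is to see whether people keep vaping once free supplies end, the free supplies need to have run out before the visit, or the analysis needs to know for whom they have not. Neither is assured. The last handout comes at week 4 itself, the practice supply is not scaled to smoking level, and later handouts are not reduced for unused pods. Anyone who vapes less than expected builds a stock, and dual users, whom the plan intends to describe, are an obvious example.

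Week-8 e-cigarette use would then combine two things: finishing leftover free pods, and obtaining pods independently. Section E says the pilot is to provide feasibility data and effect sizes for a larger trial. A persistence figure that mixes the two would be hard to interpret there, and pod counts that are not taken at the time cannot be recovered later.

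**Working it through.** The documents state no pod total, so there is no figure of the plan's own to reproduce. The check is stock arithmetic.

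**Inputs from the documents.** 7 practice pods at baseline (day −7). Five later handouts, at visits 3, 4, 5, 6 and 7 (weeks 0 to 4). One pod per pack. A minimum of 5 cigarettes a day for entry (Section G). Visit 8 on day 56, which is 28 days after visit 7.

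**Assumptions, not in the documents.** 20 cigarettes per pack; each handout equals one week's pods at the expected rate; every visit attended; no pods lost, shared or sold.

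**Formulas.** Let r = (cigarettes per day)/20, the expected pods per day.

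- Pods received: 7 + 5 × 7 × r = 7 + 35r.
- Run-out day after the switch at full expected use, practice week included (up to 20 a day): (7 + 35r)/r − 7 = 28 + 7/r.
- With use at a fraction f of the expected rate over the 63 days from baseline to visit 8, pods remain at visit 8 if 63 × f × r < 7 + 35r, that is, if f < (7 + 35r)/(63r).
- Pods left at half the expected rate: 7 + 35r − 31.5r.

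| Cigarettes per day | r | Pods received | Run-out day, full use | Pods remain at visit 8 if f is below | Pods left at f = 0.5 |
|---|---|---|---|---|---|
| 20 | 1 | 42 | 28 + 7 = 35 (week 5) | 42/63 = 0.67 | 10.5 |
| 10 | 0.5 | 24.5 | 28 + 14 = 42 (week 6) | 24.5/31.5 = 0.78 | 8.75 |
| 5 | 0.25 | 15.75 | 28 + 28 = 56 (week 8) | 15.75/15.75 = 1.00 | 7.875 |

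The period without free pods before visit 8, at full use, is therefore 56 − 35 = 21 days, 56 − 42 = 14 days and 0 days, against the 28 days that the visit schedule suggests.

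**Sensitivity to the assumptions.**

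- No pods used in the practice week: the limits become (7 + 35r)/(56r) = 0.75, 0.875 and 1.125 for 20, 10 and 5 a day. Full-use run-out moves to days 42, 49 and 63.
- Handouts rounded up to whole pods: at 10 a day, 7 + 5 × 4 = 27 pods and a limit of 27/31.5 = 0.86; at 5 a day, 7 + 5 × 2 = 17 pods and a limit of 17/15.75 = 1.08. At 20 a day nothing changes.
- Visit 7 missed, so one handout fewer: (7 + 28r)/(63r) = 0.56, 0.67 and 0.89 for 20, 10 and 5 a day.

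**Supply wording.** Handouts at weeks 0, 1, 2, 3 and 4 make five post-switch allotments plus the practice pods. The Overview in Section D describes supplies as lasting four weeks. Section A's statement that they run through four weeks after the switch fits a last handout at visit 7.

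**The case against.** Several stronger readings are tempting, and the documents do not support them.

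- *Visit 8 cannot show persistence.* Nothing is handed out in the 28 days before visit 8, so the Overview's wording is met literally. On the arithmetic above, a full switcher at 10 or more a day has two to three weeks without free pods (about one week at 10 a day if the practice pods were left untouched). Such a person still vaping at week 8 does show persistence.
- *Many participants will hold study pods.* The documents give no smoking distribution, no pod-use rates and no weekly pod quantity. The most striking case, 5 a day, is the eligibility floor. Missed visits and lost pods would shrink the stock.
- *Persistence is the only reason for the week-8 visit.* The Sub-Study overview also sets the primary outcome, CO-verified cigarette abstinence, at week 8, and Section E compares the arms on it there.
- *The arm comparison is biased by more leftover pods in the e-cigarette-only arm.* Section A predicts more quitting and exclusive switching with incentives. It does not predict more dual use without them, since non-switchers could return to cigarettes alone. Holding pods is also not the same as using them.
- *No one asks where the pods came from.* The questionnaire items are not in the documents, so a source question may exist.

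All of these limits stand. They narrow the claim but do not remove it: the handout at visit 7, the unscaled practice supply that participants keep, and the absence of any described pod count are plain in the text.

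**Conclusion.** The concern holds in a limited form. Some participants, mainly light smokers and partial or dual users, may still be using study pods at week 8, and the plan as written cannot separate that use from self-sustained use. Under the stated assumptions, pods remain at visit 8 when use is below about 67% of the expected rate at 20 cigarettes a day, 78% at 10 and 100% at 5. How many participants fall below those limits cannot be known from the documents.

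This touches a secondary, mainly descriptive outcome of a 60-person pilot. Any effect on the comparison between arms is unknown in size and direction.

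A related inconsistency sharpens the point. At baseline, participants are counselled to use only pods supplied by study staff, and no passage says that this advice ends at visit 7. Someone who followed it to week 8 could vape only leftover study pods, which is not the behaviour that the unsupplied period is meant to reveal.

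**What to change.** The change is to measurement and reporting, not to the treatment.

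1. Record pods dispensed at each visit, and unused study pods at visits 7 and 8 (by count, or by self-report if they are not brought).
2. At visit 8, ask the source of pods used in the past 7 days (study-supplied, self-obtained or both), unless the questionnaire already does.
3. In Section E, report week-8 e-cigarette use by arm, overall and split by source and by whether study pods remained. Base any statement about continued use after supplies end on that split. Counting only self-obtained pods as continued use would sit badly with the baseline counselling and would class a daily user of leftover pods as having stopped, so the overall figure should be kept.
4. Reconcile the Overview's four-week description of supplies with the handouts listed under Sub-Study Visits. Reconcile the baseline counselling on study supplies with the aim of observing use after visit 7.

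The cost is a few items and a count at existing visits, plus short edits to Sections D and E. The downside is that self-reported source and counts are imperfect, and use of self-obtained pods may be under-reported given the counselling.
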